⁸ Temperature, blood pressure and heart rate. Within each visit, preferably the same equipment shall be used for vital signs measurements. Vital signs should be assessed just before and no longer than 30 minutes before infusion start, during and after the infusions until 2 hours after end of infusions, as indicated in Section 10.5.

⁹ Optional.

Footnotes to Trial Flowchart: Cohort Expansion Part

¹⁰ One ECG will be performed at screening. Three ECGs should be performed at least 2 minutes apart before infusion of the trial drug on Visit 1 for all cycles, in accordance with the ECG Specifications Manual.

Within 4 weeks prior to Visit C1-V1. All patients will have a CT-scan with contrast of thorax, abdomen and pelvis performed as part of the screening procedure. If a CT-scan has been performed within 4 weeks prior to Visit C1-V1 as part of standard procedure, it is acceptable as screening CT-scan for the trial. If there is suggestion of brain metastases/tumors, a CT-scan of the head will be performed before inclusion.

¹² At the end of every second cycle, i.e., on Day 1 of Cycles 3, 5, 7 and 9, CT-scans can be performed up to 7 days before Day 1 of the relevant cycle to ensure result to be available before subsequent dosing. Additional scan at the EOT Visit. To be completed as indicated to confirm response, new symptoms, end of trial or physician discretion.

¹³ Patients experiencing ocular symptoms must be referred to an ophthalmologist for prompt review (preferably within 72 hours and no later than within one week).

¹⁴ Radionuclide bone scan and PSA will be performed for CRPC patients. Radionuclide bone scan will be performed at screening, every 16 weeks (i.e., Day 1 of Cycles 5 and 9), and upon clinical indication. If there is suspicion of progression, another bone scan will be performed 12 weeks later. The screening radionuclide bone scan can be performed up to 4 weeks prior to Visit C1-V1.

¹⁵ Laboratory parameters will be analyzed centrally.

¹⁶ For patients with ovarian and endometrial cancer.

¹⁷ Flow cytometry only on Cycle 1 and Cycle 5.

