8.3.4 Withdrawal and Replacement of Patients

8.3.4.1 Criteria for Patient Withdrawal from Treatment

Patients will be withdrawn from treatment for the following reasons:

- DLT/DLT-equivalent events (see Section 8.4.8 for specification, exception and dose modifications).
- > 2 dose reductions due to recurrent toxicities possibly related to tisotumab vedotin (HuMax-TF-ADC) (see Sections 8.4.5.1, 8.4.5.2, and 8.4.5.3).
- CTCAE grade \geq 3 macular-papular skin rash.
- CTCAE grade 1 treatment-related bullous dermatitis or skin bullae (blister) ≥ 0.5 cm.
- Recurrent CTCAE grade 4 neutropenia may be withdrawn, see Section 8.4.5.2.
- CTCAE grade 3 QTcF interval prolongation (≥ 501 msec on at least two separate ECGs).
- First recurrence of CTCAE grade ≥ 3 conjunctivitis (despite dose reduction, see Section 8.4.5.3)
- Third recurrence of CTCAE grade ≤ 2 keratitis (despite dose reductions, see Section 8.4.5.3)
- First occurrence of CTCAE grade \geq 3 keratitis
- Ophthalmological evaluation reveals conjunctival/corneal scarring
- Any grade of symblepharon
- Any grade of fluorescent patches or conjunctival ulceration that does not stabilize or improve after dose reduction
- Any dose delay related to ocular toxicity exceeding 12 weeks

Final 5.0 (incorporating Protocol Amendment 4) 06 Jul 2017

- Dose delay of more than two weeks due to toxicity possibly related to tisotumab vedotin (HuMax-TF-ADC) (except for dose delays due to neuropathy, skin rash, keratitis and conjunctivitis)*.
- Pregnancy.
- Patient choice.
- Investigator or sponsor decision.
- * The exception is due to the fact that decrease to CTCAE grade 1 intensity for neuropathy, skin rash, keratitis and conjunctivitis may last for more than two weeks.

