8.4.5.3 Dose Modifications and Mitigation Plan for Ocular Adverse Events

Events of conjunctivitis and keratitis have been reported in patients treated with tisotumab vedotin (HuMax-TF-ADC). To prevent occurrence and ensure appropriate handling, events should be prevented and managed as described below.

Final 5.0 (incorporating Protocol Amendment 4) 06 Jul 2017

Preventive measures for all patients:

- Use of preservative-free lubricating eye drops from the start of trial treatment until the end of treatment.
- Avoid use of contact lenses while treated with tisotumab vedotin (HuMax-TF-ADC).
- Use of refrigerator-based eye cooling pads during infusion, e.g. THERA PEARL Eye Mask or similar. To be applied immediately before infusion in accordance with the instructions provided with the eye cooling pads.
- Administration of local ocular vasoconstrictor before infusion (brimonidine tartrate 0.2% eye drops or similar, 3 drops in each eye immediately prior to start of infusion; otherwise to be used in accordance with the product prescribing information). If the patient does not tolerate ocular vasoconstrictors due to adverse reactions, continued treatment with these may be stopped at the discretion of the investigator and following discussion with the Genmab Medical Officer.
- Application of steroid eye drops for 3 days from the day of infusion (dexamethasone 0.1% eye drops or equivalent, 1 drop in each eye 3 times daily for 3 days [first drop to be given before start of infusion], otherwise to be used in accordance to product prescribing information).

In case of any ocular symptoms:

Conjunctivitis:

Grading: All events of conjunctivitis should be graded according to both:

- Ophthalmological grading based on the objective eye-examination findings performed by the ophthalmologist.
- CTCAE grading system based on National Cancer Institute Common Terminology Criteria for Adverse Events (NCI-CTCAE) version 4.03 (NCI-CTCAE v4.03, 2010) assessed by the investigator.

Dose delay and dose modification:

- CTCAE grade 1 conjunctivitis: Hold dosing until the event is managed effectively by topical treatment initiated by the ophthalmologist (according to treatment guidelines below). When the event is managed effectively the patient can be re-treated with the same dose of trial drug as being administered prior to the event onset.

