10.7 Computerized Tomography

All patients will have a CT-scan with contrast of thorax, abdomen and pelvis performed during screening. If there is suggestion of brain metastases/tumors, a CT-scan of the head will be performed before inclusion.

Up to five target lesions (maximum two per organ) will be defined at screening and these must be followed throughout the trial. Non-target lesions will also be assessed throughout the trial.

Final 5.0 (incorporating Protocol Amendment 4) 06 Jul 2017

Scans will be repeated every six weeks (at the end of every second cycle) during the trial period. If the result is PR or better, CT-scan should be repeated after four weeks to confirm response. CT-scans can be performed up to seven days before Day 1 of the relevant cycle to ensure results are available before subsequent dosing.

Additional CT-scans may be performed at the investigators' discretion to confirm response or new symptoms. In this case, the investigator must choose the imaging technology based on the clinical indication.

Magnetic resonance imaging can be performed instead of a CT-scan if the patient is allergic to iodine contrast or at the discretion of the investigator, after approval of the sponsor.

The reading of the surveys will be done by a radiologist. Sites should attempt to maintain the same radiologist throughout the trial. The overall interpretation of the evaluation shall be recorded in the eCRF and a copy of the evaluation reports should be kept in the patient's file.

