12.5.3.3 Progression-free Survival

Progression-free survival is defined as the number of days from Day 1 in Cycle 1 to first PD or death. Progression-free survival will be derived for all patients and presented graphically as well as summarized using survival analysis methods.

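### CT timing after the urgent safety measure is fixed both by treatment cycle and by six-week interval, and the plan does not say which governs during a toxicity hold

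*Protocol*

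**What the plan says.** Two places set the CT schedule for patients on the 21-day cycle. Table 5 footnote 12 (Section 8.1.1) puts it "At the end of every second cycle, i.e., on Day 1 of Cycles 3, 5, 7 and 9". Section 10.7 says "Scans will be repeated every six weeks (at the end of every second cycle) during the trial period". The only window looks backwards from the dosing day: "CT-scans can be performed up to seven days before Day 1 of the relevant cycle to ensure results are available before subsequent dosing".

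The dosing day can move. Section 8.4.5.3 requires a hold even at the lowest grade: "CTCAE grade 1 conjunctivitis: Hold dosing until the event is managed effectively by topical treatment initiated by the ophthalmologist". Keratitis of grade 2 or lower is also held. Section 8.3.4.1 makes withdrawal from treatment mandatory for "Any dose delay related to ocular toxicity exceeding 12 weeks", so shorter ocular holds are compatible with staying on treatment. The general two-week limit on toxicity delays applies "except for dose delays due to neuropathy, skin rash, keratitis and conjunctivitis"; no upper limit is stated for neuropathy or rash.

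Section 12.5.3.3 defines the endpoint: "Progression-free survival is defined as the number of days from Day 1 in Cycle 1 to first PD or death". Section 12.5.3.4 ends duration of response at the same event, and Section 12.5.3.5 summarises the percentage of patients without progression after four cycles.

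**The concern.** Progression on imaging can be recorded only when a scan is done. If the scan waits for Day 1 of a given cycle, and Day 1 waits for an eye, nerve or skin event to settle, then toxicity sets the assessment clock. Patients with toxicity would be looked at later than the others, and the extra time without a scan falls while they are off drug. Their progressions would on average be dated later. If some sites read the schedule by cycle and others by calendar, the timing would also differ between sites for reasons unrelated to disease.

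Prolonged holds are foreseeable: severe ocular toxicity is the reason for Amendment 4, and Section 8.3.4.1 explains its exemptions by saying that recovery may take more than two weeks. Scans that were not taken cannot be recovered by a later analysis, so the point belongs in the protocol.

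**Working it through.** **The plan's own figure.** Two cycles of 21 days are 42 days, or 6 weeks. Nine cycles are 9 × 21 = 189 days, or 27 weeks, as Section 8.1 states. The six-week interval reproduces when there is no delay.

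**The gap with a hold.** If scans follow delayed cycles, one hold of h weeks makes the affected gap 6 + h weeks: 9 for h = 3, 12 for h = 6, and 18 for h = 12, the longest ocular delay before mandatory discontinuation.

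**Illustration of detection delay.** These are assumptions, not document figures: exponential progression with median 12 weeks; one hold, in Cycle 1; scans every 6 weeks after the first; no deaths and no unscheduled scans. Then λ = ln 2/12, 1/λ = 17.31 weeks, and 6/(1 − e^(−6λ)) = 20.49 weeks. With the first scan at week a, mean delay from progression to recording is a + S(a) × 20.49 − 17.31, where S(a) is the proportion not yet progressed.
- No hold (a = 6): 6 + 0.7071 × 20.49 − 17.31 = 3.2 weeks.
- Six-week hold (a = 12): 12 + 0.5 × 20.49 − 17.31 = 4.9 weeks.
- Twelve-week hold (a = 18): 18 + 0.3536 × 20.49 − 17.31 = 7.9 weeks.

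**A fixed-week reading under the same assumptions.** At week 12, true progression-free is 50%.
- Twelve-week hold in 20% of patients: 0.2 × 100% + 0.8 × 50% = 60% recorded. In 40%: 0.4 × 100% + 0.6 × 50% = 70%.
- Three-week hold: held patients read S(9) = 59.5%, which adds 1.9 points at 20% held and 3.8 points at 40%.
- Six-week hold: no difference at week 12, because both schedules scan then.

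The 60% and 70% are an extreme: the longest ocular hold, at the earliest time, read at a week inside the gap. At week 18, when both schedules scan, that same 12-week hold makes no difference.

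**A wider set of scenarios.** Simulation with true medians of 12, 18 or 26 weeks, and one hold of 3, 6 or 12 weeks before one of Cycles 2 to 5, in 10%, 25% or 50% of patients (27 combinations, all assumed), compared cycle-based with six-weekly calendar scans.

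| Result | Range |
|---|---|
| Mean shift in recorded PFS, held patients | 0.3 to 4.1 weeks later |
| Mean shift, all patients | 0.03 to 2.0 weeks later; below 0.5 in 19 of 27 |
| Recorded progression-free beyond week 12 | about 1 to 18 points higher |

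Example: median 18 weeks, 25% held for 12 weeks. The proportion beyond week 12 goes from 63.0% to 69.7%, with a mean shift over all patients of 0.8 weeks. The mean shift was upward in every combination, although an individual patient can move either way.

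**The other two outcomes.** Four cycles end at 4 × 3 = 12 weeks without delay and at 12 + 12 = 24 weeks with a 12-week hold. With a 12-week median, 50% are progression-free at week 12 and 25% at week 24. Read at that visit, held patients could therefore look worse. Duration of response starts at first documented response, so a late scan can delay both its start and its end.

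**The case against.** The strongest reply is that no sentence says the CT moves with a hold, and three provisions point the other way. Section 10.7 states six weeks. Table 5 footnote 4 places Visit 1 of Cycle 2 onwards 7 ± 3 days after Day 15 of the previous cycle, with no exception for holds. Section 9 says treated patients are followed per protocol however many doses they receive, with missed evaluations done as near as possible to the original schedule. This stands in part: a site following the six-week wording would not slip. But Section 10.7 equates its interval with the end of every second cycle, and neither Section 9 nor footnote 4 says which clock applies while dosing is held. The conflict is unresolved.

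Extra CT at the investigator's discretion, the End of Trial scan, and deaths (which are PFS events) would all soften the effect, and none is in the calculations. They do not schedule an assessment during a hold.

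A reader might infer more than the documents support:
- **That PFS is overstated as a matter of fact.** This depends on which wording sites follow and on how often and how long doses are held, which the protocol does not quantify.
- **That all progression-based summaries are inflated.** The direction is open for duration of response and for the four-cycle summary.
- **That a comparison or error rate is compromised.** PFS is a secondary endpoint and Section 12.3 plans no formal tests. Section 12.7 lists no subgroup by ocular toxicity, so a spurious link between toxicity and longer PFS would arise only in an unplanned analysis. Any reporting by dosing schedule is left to the SAP.

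**Conclusion.** The point holds as an unresolved conflict between a cycle-based and a calendar-based CT schedule. It is not a demonstrated overstatement of PFS. Where the cycle-based wording is followed, one 12-week ocular hold widens the planned scan gap from 6 to 18 weeks, and recorded PFS in held patients tends on average to be later. Over the whole group the shift may be small. The arithmetic on the gap rests only on the protocol's own figures; every estimate of effect on PFS rests on assumed progression times, hold rates and hold lengths. The consequence is limited to descriptive secondary results, but the correction is cheap and should be made.

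**What to change.** In Table 5 footnote 12, and in Section 10.7 for patients on the 21-day cycle, state that CT is performed every 6 weeks from Cycle 1 Day 1, irrespective of dose holds, delays or cycle number, and remove the tie to Day 1 of Cycles 3, 5, 7 and 9. Where a dose is planned, keep the window of up to 7 days before the scheduled date. A symmetric window would let a scan fall after the dose that its result is meant to precede. In reporting, flag progressions first seen after a scan gap longer than planned; scan dates will already be in the listings, since Section 12.3 lists all data.

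The cost is one footnote and one sentence. Some scans will fall outside dosing visits, and a patient held for a long time may have one or two scans more than under the cycle-based schedule. Dosing and hold rules are unchanged.

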7.2.2 Secondary Endpoints

- Safety laboratory parameters (hematology, biochemistry, coagulation factors and flow cytometry)
- Skin disorders
- Bleeding events
- Neuropathy
- PK parameters (clearance, volume of distribution and AUC [AUC0-Clast and AUC0-∞], Cmax, time of Cmax [Tmax], pre-dose values, and half-life of tisotumab vedotin (HuMax-TF-ADC) and free toxin [MMAE])
- Immunogenicity of tisotumab vedotin (HuMax-TF-ADC) (human anti-human antibodies)
- Anti-tumor activity measured by tumor shrinkage (based on CT-scan evaluations), change in PSA and CA 125
- Objective Response (Complete Response [CR] or PR), Disease Control (CR, PR or SD), Progression-Free Survival (PFS) and Duration of Response (DoR)

Final 5.0 (incorporating Protocol Amendment 4) 06 Jul 2017

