¹⁶ For patients with ovarian and endometrial cancer.

¹⁷ Flow cytometry only on Cycle 1 and Cycle 5.

¹⁸ HBsAg, anti-HBs and anti-HBc, Hepatitis C and antibodies to CMV antigen will be assessed at screening for all patients; for CMV, anti-IgG and IgM will be assessed and, in case of positive IgM, it will be confirmed with CMV PCR; for HCV, anti-IgG will be assessed and, if positive, it will be confirmed with HCV PCR. HPV only for patients with cervical cancer. At EOT, only antibodies to CMV antigen will be assessed.

¹⁹ See Table 4 and Section 10.17 for details of PK samplings.

²⁰ Archived biopsy material can be forwarded if a sample is available. If no sample is available, a new tumor biopsy must be obtained at least 2 weeks before dosing to ensure healing of wound.

²¹ Only on Cycle 4.

²² Preventive eye therapy to be administered in relation to infusions as detailed in Section 8.4.5.3.

Table 4: PK Sampling - Cohort Expansion Part - SUPERSEDED

Treatment Cycle	Screening			Cycle 1				Cycle 2-9		Unscheduled
Visit Number	0	1	2	3	4	5	1	2	3	1-X
Day/Week	-	1d	8d	15d	18d	22d	1d	8d	15d	
Before Infusion (on infusion days)	X	X	X	X	X	X	X	X	X	X^2
End of infusion (+15 minutes) ¹		X					X			
+ 2 hours (± 15 minutes) after end of infusion ¹		X								

¹ Allowed time windows are indicated in parentheses.

² Optional.

 Table 5:
 Trial Flow Chart – Cohort Expansion Part - After Urgent Safety Measure

Treatment Cycle	Screening		Cycle 1			Cycle 2-9	1	EOT ¹	Withdrawal Safety Follow-up ²	Unscheduled
Visit Number	0	13	2	3	1 ³	2	3	-	-	1-X
Day/Week	≤ 21 days prior to Visit C1-V1	1d	8d	15d	1d	8d	15d	-	30 days after last dosing	-
Visit window ⁴		-	±1d	±1d	±3d	±1d	±1d	-	±14d	-
Informed Consent	X ⁵									
Eligibility Criteria	X									
Demographics	X									
Medical History ⁶	X									
Height and Body Weight ⁷	X	X			X			X		
Physical Examination	X	X						X		
Vital Signs ⁸	X	X	X	X	X		X	X		X^9
ECG ¹⁰	X	X			X			X		X^9
CT-Scan	X ¹¹				X^{12}			X^{12}		X^9
ECOG Performance Status	X	X			X			X		X ⁹
Adverse Events	X	X	X	X	X		X	X	X	X ⁹
Concomitant Medication	X	X	X	X	X		X	X		X^9
Trial Drug Administration ²²		X			X					
Bleeding Assessment	X	X		X	X			X		X
Skin Assessment	X	X		X	X			X		X
Neuropathy Assessment	X	X		X	X			X		X
Ophthalmological Evaluation	X			X^{13}			X^{13}	X ¹³		X^{13}
Radionuclide Bone Scan ¹⁴	X				X					X^9
LABORATORY ASSESSMENT	Γ S ¹⁵									
Hematology	X	X	X	X	X	X	X	X		X^9
Biochemistry	X	X	X	X	X	X	X	X		X^9
Coagulation factors	X	X	X	X	X	X	X	X		X^9

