¹⁸ HBsAg, anti-HBs and anti-HBc, Hepatitis C and antibodies to CMV antigen will be assessed at screening for all patients; for CMV, anti-IgG and IgM will be assessed and, in case of positive IgM, it will be confirmed with CMV PCR; for HCV, anti-IgG will be assessed and, if positive, it will be confirmed with HCV PCR. HPV only for patients with cervical cancer. At EOT, only antibodies to CMV antigen will be assessed.

¹⁹ See Table 4 and Section 10.17 for details of PK samplings.

²⁰ Archived biopsy material can be forwarded if a sample is available. If no sample is available, a new tumor biopsy must be obtained at least 2 weeks before dosing to ensure healing of wound.

²¹ Only on Cycle 4.

²² Preventive eye therapy to be administered in relation to infusions as detailed in Section 8.4.5.3.

Table 6: PK Sampling - Cohort Expansion Part - After Urgent Safety Measure

Treatment Cycle	Screening		Cycle 1			Cycle 2-9		Unscheduled
Visit Number	0	1	2	3	1	2	3	1-X
Day/Week	-	1d	8d	15d	1d	8d	15d	
Before Infusion (on infusion days)	X	X	X	X	X	X	X	X^2
End of infusion (+15 minutes) ¹		X			X			
+ 2 hours (± 15 minutes) after end of infusion ¹		X						

¹ Allowed time windows are indicated in parentheses.

² Optional.

Final 5.0 (incorporating Protocol Amendment 4) 06 Jul 2017

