10.17 Pharmacokinetic Assessments

Blood samples for assessment of tisotumab vedotin (HuMax-TF-ADC) and MMAE will be drawn for central analysis in accordance to the timing provided in Table 2 and Table 4 according to the initially designed treatment scheme, and in Table 6 after implementation of the urgent safety measure (Protocol Amendment 4.0). Two assays will be used for tisotumab vedotin (HuMax-TF-ADC), one detecting tisotumab vedotin (HuMax-TF-ADC) only and one detecting tisotumab vedotin (HuMax-TF-ADC) and non-conjugated Humax-TF.

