12.5.6 Statistical Analysis of Pharmacokinetics Data

Individual curves of plasma/serum concentration of tisotumab vedotin (HuMax-TF-ADC), HuMax-TF and free toxin (MMAE), including information on actual dose, will be presented for all patients. All available data will be shown in these figures.

The following PK parameters will be calculated based on non-compartmental methods: clearance, volume of distribution and AUC (AUC_{0-7days} and AUC_{0-∞}), C_{max}, T_{max}, pre-dose values, and half-life. The PK parameters will be calculated separately for Cycle 1 and Cycle 2.

The relation between derived PK parameters and covariates such as actual dose, weight and dose, and selected laboratory parameters will be evaluated graphically.

If deemed applicable compartmental modeling approaches to parameter estimation will be applied.

Further exploratory analyses of PK data may be performed.

Final 5.0 (incorporating Protocol Amendment 4) 06 Jul 2017

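### Table 6 leaves no PK sample between 2 h after infusion and Day 8, so non-compartmental Cmax and Tmax of MMAE cannot be validly derived for q3wk patients

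*Protocol*

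**What the plan says.** Section 7.2.2 lists clearance, volume of distribution and AUC, and then "Cmax, time of Cmax [Tmax], pre-dose values, and half-life of tisotumab vedotin (HuMax-TF-ADC) and free toxin [MMAE", as secondary endpoints. MMAE is thus covered on the same footing as the conjugate.

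Section 12.5.6 fixes the method: "The following PK parameters will be calculated based on non-compartmental methods", with Cmax and Tmax in the list and results for Cycle 1 and Cycle 2 separately. Compartmental modelling is allowed there only if deemed applicable.

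Section 10.17 directs samples for the conjugate and MMAE to Tables 2 and 4 under the original scheme, "and in Table 6 after implementation of the urgent safety measure (Protocol Amendment 4.0"). That last table, headed "Table 6: PK Sampling - Cohort Expansion Part - After Urgent Safety Measure", schedules these samples:

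- **Cycle 1:** Day 1 before infusion, at end of infusion and at "2 hours (± 15 minutes) after end of infusion", then Days 8 and 15.
- **Cycles 2-9:** Day 1 before infusion and at end of infusion, then Days 8 and 15.

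Section 9.2.2.3 confirms that visits fall on Days 1, 8 and 15 only. Footnote 19 to the PK row of Table 5, the post-amendment flow chart, reads "See Table 4 and Section 10.17 for details of PK samplings". Table 4 is the schedule marked as superseded.

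**The concern.** A non-compartmental Cmax is the highest sampled concentration, and Tmax is the time of that sample. Both are meaningful only if sampling surrounds the peak. For the conjugate, in so far as it peaks near end of infusion, Table 6 does this. MMAE is different. Section 8.4 describes it as bound through a protease-cleavable linker, so it is formed after dosing and should peak later than the conjugate. That is where Table 6 has no samples.

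The regimen was changed because of severe ocular toxicity, so peak free-toxin exposure under q3wk is a figure readers will want to set against toxicity and against the earlier schedule. A Cmax read from the edge of a week-long gap could understate exposure by an unknown factor, and Tmax would describe the visit calendar rather than the drug.

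**Working it through.** **1. The gap.** Assume the minimum 30-minute infusion and count from its start.

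- Cycle 1: last Day 1 sample at 0.5 + 2 = 2.5 h, next at 7 × 24 = 168 h. Gap 168 − 2.5 = 165.5 h, or about 141 to 190 h with the visit windows.
- Cycles 2-9: last Day 1 sample at 0.5 h. Gap 168 − 0.5 = 167.5 h.

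Observed Tmax can only be end of infusion, +2 h (Cycle 1 only), Day 8, Day 15 or the next pre-dose sample.

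**2. What the three schedules offer.**

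| Schedule | Cycle 1 samples inside the window | Cycle 2 |
|---|---|---|
| Table 2, Dose Escalation | Days 2 and 16 (24 h after a dose), Day 18 (72 h) | none |
| Table 4, superseded expansion | Day 18 only (72 h after the Day 15 dose) | none |
| Table 6, current | none | none |

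The amendment removed one sample, Cycle 1 Day 18, and put nothing in its place. The gap after the Day 1 dose, and the gap in Cycle 2, were already in Table 4.

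**3. How much it could matter.** The documents give no half-lives and no MMAE Tmax, so the following ranges are assumptions: conjugate 2, 3, 4 or 5 days; MMAE 0.5, 1, 2 or 3 days (16 combinations). The model has first-order release and first-order elimination after a single dose, with kp = ln 2 / conjugate half-life and km = ln 2 / MMAE half-life:

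C(t) ∝ kp/(km − kp) × [exp(−kp·t) − exp(−km·t)], peak at t = ln(km/kp)/(km − kp).

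Where kp = km, use the limit kp·t·exp(−kp·t), with its peak at 1/kp.

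Worked case, conjugate 3 d and MMAE 1 d:

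- kp = 0.231 and km = 0.693 per day; peak at 1.099/0.462 = 2.38 d.
- C(peak) = 0.5 × (0.577 − 0.192) = 0.192.
- C(7 d) = 0.5 × (0.198 − 0.008) = 0.095; C(2.5 h) = 0.023.
- Highest Table 6 value / true peak = 0.095/0.192 = 50%, recorded at 7 d instead of 2.38 d.

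Highest Cycle 1 value under Table 6 as a percentage of the true peak, with the true peak time in brackets:

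| Conjugate half-life | MMAE 0.5 d | 1 d | 2 d | 3 d |
|---|---|---|---|---|
| 2 d | 21 (1.3 d) | 32 (2.0 d) | 58 (2.9 d) | 74 (3.5 d) |
| 3 d | 34 (1.5 d) | 50 (2.4 d) | 74 (3.5 d) | 87 (4.3 d) |
| 4 d | 46 (1.7 d) | 61 (2.7 d) | 84 (4.0 d) | 94 (5.0 d) |
| 5 d | 54 (1.8 d) | 69 (2.9 d) | 89 (4.4 d) | 97 (5.5 d) |

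The true peak lies in the gap in all 16. Recorded Tmax is 7 d in 15 and 2.5 h in the other (2 d with 0.5 d). Adding samples at 24 h and 72 h would recover 91-100% of the peak; 72 h alone would recover 72-100%.

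**4. Wider range.** With conjugate 1-6 d and MMAE 0.25-2.5 d (20 combinations), the true peak is at 0.7-5.4 d, again always in the gap. Table 6 recovers 18-97% in Cycle 1 and as little as 6% in Cycle 2, where the +2 h sample is missing (single-dose model, no carry-over). The Table 2 pattern after the Day 15 dose recovers 91-100%.

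**The case against.** **Deferral to the SAP.** Section 12.1 says the SAP will be updated for patients treated after Amendment 4, Section 12.3 leaves reporting by dosing schedule to it, and Section 12.5.6 already permits compartmental modelling. The SAP may therefore deal with this. But the protocol itself fixes the endpoint, the sampling times and the non-compartmental method, and those three do not fit together. Modelling is only an option, and q3wk data alone carry no information inside the gap.

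**The PK objective still reads 3q4wk.** Section 7.1.2 says the objectives are unchanged. That is true, but Section 10.17 continues MMAE sampling under Table 6 and the endpoint list is not limited by regimen.

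**Thin support for the size.** This stands. The half-lives are assumed, and in 7 of the 16 scenarios Table 6 captures at least 74% of the peak. The Introduction is blank in the public copy, so any earlier PK knowledge behind the sparse schedule cannot be checked.

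**What the amendment removed.** A reader might infer that it deleted both the 24 h and the 72 h samples and so created the gap. Table 4 does not support that: it had no 24 h sample. Nor can a lower q3wk peak simply be put down to lost samples. Within the expansion part the difference is one sample after a third weekly dose, and 1.2 mg/kg three times against 2.0 mg/kg once already differs in dose and accumulation.

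**Limited role.** PK is secondary and descriptive, with no formal tests.

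**Conclusion.** The point holds in this form: under Table 6, observed MMAE Cmax and Tmax cannot be validly derived for q3wk patients in either cycle that Section 12.5.6 analyses. The gap itself is read directly from the schedule. That the MMAE peak falls inside it is an inference from linker release, in keeping with the 24 h and 72 h sampling in Table 2. Under the assumed half-lives the Cmax bias runs from severe (21% recovered) to negligible (97%), while Tmax is wrong in every scenario.

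Two firmer readings are tempting and go too far. One is that nothing can be derived: a program will return a maximum, but not a valid one. The other is that Cmax will certainly come out too low with a Tmax of about 7 days: that depends on half-lives the documents do not give.

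The footnote 19 reference is a separate slip. It conflicts with Sections 8.1.1 and 10.17 and sends sites to a table with Days 18 and 22, which Table 5 lacks, but it adds no weight to the Cmax argument.

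**What to change.** In Section 12.5.6, state that observed MMAE Cmax and Tmax will not be reported from Table 6 data, nor compared with 3q4wk values obtained under denser sampling. Report MMAE concentrations from Table 6 at nominal times: end of infusion, +2 h in Cycle 1, Day 8, Day 15 and pre-dose. Give the q3wk peak and time to peak only as compartmental-model estimates, informed by the Dose Escalation samples on Days 2, 16 and 18, and label them as such. Carry the same wording into the SAP update.

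Correct Table 5 footnote 19 to refer to Table 6.

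The cost is a few sentences, one footnote and the modelling work; no visit or sample is added. The downside is that the q3wk MMAE peak becomes a model-based estimate, resting on the assumption that release and elimination seen under 3q4wk carry over to q3wk.
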